### **Non-sensor based clinical**

For the insulin dose data, ANCOVA will again be used. Analysis will be adjusted for the baseline value of the outcome measure, the baseline HbA1c and the other variables included in the minimisation allocation algorithm. This analysis will be repeated to compare the two intervention groups for the insulin dose data obtained both at 12 weeks and at 24 weeks following randomisation.

Safety data, including number of severe hypoglycaemia events and number of ketone-positive hyperglycaemia, will be tabulated for all participants, including drop-outs and withdrawals, irrespective of whether CGM data are available and irrespective of whether closed-loop was operational. Severe hypoglycaemic events and ketone-positive hyperglycaemia will be tabulated in each treatment group.

### **Non-sensor based patient-reported (psychosocial)**

ANCOVA will also be used for the psychosocial outcome data evaluation, with trial arm effect as the focus, adjusting for baseline level of the outcome and the other baseline variables included in the minimisation allocation algorithm as covariates.

In addition, analysis for caseness will be performed for the PHQ-9 and the T1DDS outcomes, by the use of logistic regression models, with trial arm effect as the focus, adjusting for baseline caseness of the outcome and the other baseline variables included in the minimisation allocation algorithm as covariates. Caseness for the PHQ-9 is defined as score of 10 or above, and for the T1DDS as 2 or above.

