12.2 Questionnaires

12.2.1 Questionnaires

Quantitative data on health-related quality of life, diabetes distress, needle burden, disordered eating, depression and diabetes treatment satisfaction will be assessed using validated questionnaires. Participants will complete the questionnaires at screening and at the end of the study intervention. All results will be evaluated at the end of the study.

List of questionnaires are:

1. EQ-5D-5L questionnaire (Appendix 1)
2. The Glucose Monitoring Satisfaction Survey (GMSS) (Appendix 2).
3. Patient Health Questionnaire (PHQ-9) (Appendix 3)
4. Diabetes Treatment Satisfaction Questionnaire (DTSQ) (Appendix 4)
5. Diabetes fear of injecting and self-testing questionnaire (D-FISQ) (Appendix 5)
6. Diabetes Eating Problem Survey (DEPS-R) (Appendix 6)
7. Type 1 Diabetes Distress Scale (DDS) (Appendix 7)
8. The Clarke questionnaire and Gold score. (Appendix 8)
9. Additional non-validated questionnaires for subset of participants in the FSL2 arm (Appendix 10 and 11) and clinical investigators (Appendix 12) exploring expectations and experience of using FSL2 during the study

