##### Baseline characteristics:

- Centre (Birmingham; Cambridge; Derby; Manchester; Norwich; Portsmouth; Ipswich; Wareham/Poole)
- HbA1c
- HbA1c category (7.5%-9.0%; >9.0%-11%)
- Duration of diabetes
- Treatment modality (MDI; CSII)
- Prior participation in structured education course (yes; no)
- Current use of bolus calculator (yes; no).
- BMI
- Ethnicity (White; Mixed; Asian/Asian British; Black/African/Caribbean /Black British; Other; Prefer not to answer; Not assessed)
- Deprivation decile
- Age
- Sex (male; female)
- Education (< Bachelor's degree; >= Bachelor's degree)
- Occupation (Office based; Manual; No Occupation)
- History of Diabetes complications:
  - o Retinopathy (past; current; no)
  - o Neuropathy: including peripheral, autonomic, and diabetic gastroparesis (yes; no)
  - o Microalbuminuria or Renal impairment (yes; no)
- Use of any lipid-lowering agents (yes; no)
- Use of any anti-hypertensive agents (yes; no)
- Current Insulin therapy (Treatment modality: Multiple Daily Injection; Insulin Pump Therapy)

- History of disordered eating (yes; no)
- History of needle phobia (yes; no)
- Type 1 Diabetes Distress Scale (T1-DDS) mean-item score
- T1-DDS average-item score category ( $\geq 1.0 - 1.5$ ;  $\geq 1.5 - 2.0$ ;  $\geq 2.0 - 3.0$ ;  $\geq 3.0 - 6.0$ )
- Patient Health Questionnaire (PHQ-9) total score
- PHQ-9 items sum score category ( $< 5$ ;  $\geq 5 - 10$ ;  $\geq 10 - 15$ ;  $\geq 15 - 20$ ;  $\geq 20 - 27$ )
- Diabetes fear of injecting and self-testing questionnaire (D-FISQ) total score
- The revised Diabetes Eating Problem Survey (DEPS-R) total score
- Diabetes Treatment Satisfaction Questionnaire (DTSQ) total score
- The Glucose Monitoring Satisfaction Survey (GMSS) mean-item score, and subscales mean-item score:
  - o Openness
  - o Emotional burden
  - o Behavioural burden
  - o Trust
- Hypoglycaemia burden assessed using:
  - o Clarke score
  - o Gold score
  - o Number with 1 or more severe hypoglycaemia episodes in last 6 months and 12 months
- Concomitant Diabetes Medications:
  - o GLP-1 analogues (yes; no)
  - o Metformin (past; current)
  - o SGLT2 inhibitor (yes; no)

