### 5.2.2 Secondary outcome analysis

#### HbA1c based

For the HbA1c 12-week outcome, an ANCOVA model will be used, with trial arm effect as the focus, with adjustment for baseline HbA1c and the other baseline variables included in the minimisation allocation algorithm as covariates.

For the HbA1c-based [yes/no] variables, logistic regression models will be used. For each model, trial arm effect will be the focus, with adjustment for the baseline HbA1c and the other variables included in the minimisation allocation algorithm as covariates.

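### The supplementary PHQ-9 and T1-DDS caseness models adjust for baseline case status when the baseline score is available, which gives up a little power

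*SAP*

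**What the plan says.** SAP 5.2.2, under the patient-reported (psychosocial) outcomes, sets out two analyses of PHQ-9 and T1-DDS.

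- ANCOVA on the scores, "adjusting for baseline level of the outcome and the other baseline variables included in the minimisation allocation algorithm as covariates".
- As an addition, logistic regression for caseness, "adjusting for baseline caseness of the outcome" and for the other minimisation variables. The cut-offs follow: "Caseness for the PHQ-9 is defined as score of 10 or above, and for the T1DDS as 2 or above".

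The underlying scores exist at baseline. Protocol 12.2.1 states: "Participants will complete the questionnaires at screening and at the end of the study intervention". SAP 4.5 lists both "Patient Health Questionnaire (PHQ-9) total score" and "Type 1 Diabetes Distress Scale (T1-DDS) mean-item score" among the baseline characteristics.

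Caseness is not among the psychosocial outcomes listed in SAP 5.1.2, and Protocol 14.2.2 has no caseness analysis. The SAP gives no reason for using a binary baseline covariate in these models.

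**The concern.** Splitting a prognostic covariate at a cut-off discards the information on either side of it. With PHQ-9 cut at 10, participants who enter with scores of 0 and 9 count as alike, while those with 9 and 10 count as different. Dichotomising the outcome already costs power, and dichotomising the baseline adds a second loss that can be avoided. At stake is the precision of two supplementary between-arm comparisons. The validity of the test is not in question.

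**Working it through.** **The plan's own figure.** The documents state no power for the caseness models. The only stated power is for HbA1c (Protocol 14.1, SAP 2.3): difference 0.4, SD 0.8, two-sided 5%, 64 per arm, 80%. By normal approximation, n per arm = 2 × (1.960 + 0.842)² × (0.8/0.4)² = 62.8, so 63. At 64 per arm power is 80.7% (normal) or 80.1% (t). With 15% attrition, 128/0.85 = 150.6. The figure reproduces, and 64 per arm is carried forward.

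**Inputs from the documents.** 64 per arm, 1:1 allocation, two-sided 5%, logistic regression.

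**Inputs assumed.** Correlation ρ of 0.5 to 0.8; baseline caseness π of 30% or 50%; arm shift d of 0, 0.3 or 0.5 SD.

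**Model.** Baseline X ~ N(0,1). Follow-up Y = ρX + √(1−ρ²)·ε − d·arm. A participant is a case if the score is at or above c = Φ⁻¹(1−π), which is 0.524 for 30% and 0 for 50%. Fit logit P(case at follow-up) = β₀ + β₁·arm + β₂·B, with B either baseline caseness or baseline score, and reject if |β₁/SE| > 1.96. There were 4,000 simulated trials per setting. The standard error of a single power near 60% is √(0.6 × 0.4/4000) = 0.8 points. Both models were fitted to the same simulated data, so their difference is more precise than that suggests.

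**Power (%), baseline caseness → baseline score:**

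| ρ | Caseness | Shift 0.3 SD | Shift 0.5 SD | ANCOVA on score, 0.5 SD |
|---|---|---|---|---|
| 0.5 | 30% | 24.9 → 26.0 (+1.1) | 55.8 → 57.2 (+1.4) | 90.3 |
| 0.5 | 50% | 31.2 → 32.2 (+1.0) | 64.5 → 67.0 (+2.5) | 89.4 |
| 0.6 | 30% | 26.1 → 28.1 (+2.0) | 56.4 → 60.6 (+4.2) | 93.1 |
| 0.6 | 50% | 31.6 → 33.1 (+1.5) | 67.1 → 71.2 (+4.1) | 94.2 |
| 0.7 | 30% | 28.2 → 31.4 (+3.2) | 60.9 → 66.0 (+5.1) | 98.0 |
| 0.7 | 50% | 33.4 → 37.1 (+3.7) | 70.5 → 75.8 (+5.3) | 97.6 |
| 0.8 | 30% | 30.6 → 35.0 (+4.4) | 64.9 → 72.4 (+7.5) | 99.6 |
| 0.8 | 50% | 36.7 → 42.0 (+5.3) | 76.2 → 83.6 (+7.4) | 99.6 |

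The ANCOVA does not depend on the caseness rate, so differences within a value of ρ in the last column are simulation noise.

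**Type I error (d = 0).** 4.4% to 5.6% across both adjustments.

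**What baseline caseness already recovers.** At ρ = 0.7, caseness 30% and shift 0.5 SD, power is 52.1% with no baseline covariate, 60.9% with caseness and 66.0% with the score. Caseness therefore captures 60.9 − 52.1 = 8.8 of the 66.0 − 52.1 = 13.9 points available.

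**Skewed baseline score entered linearly** (caseness 30%, shift 0.5 SD): 55.9% → 58.4% at ρ = 0.6 and 59.8% → 64.9% at ρ = 0.7.

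**With minimisation covariates.** The runs above omit the other covariates that the SAP requires. Two further sets of runs with stand-ins for them gave similar results.

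- ρ 0.5 to 0.8: gains of about 1 to 6 points at 0.5 SD, about 0.5 to 6 points at 0.3 SD, and about 1 to 3 points with a skewed score. Type I error was 4.7–6.0% with caseness and 5.3–6.3% with the score.
- ρ 0.5 to 0.7, 1,500 trials per setting: gains of 1.8 to 5.2 points at 0.5 SD, 0.6 to 3.7 at 0.3 SD and 0.3 to 1.4 at 0.2 SD.

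**The case against.** **These models are supplementary.** This stands. The continuous information that the caseness models drop is used in the ANCOVA on the same scales, which has about 89% to 99.6% power at a 0.5 SD shift in the table. The caseness models carry no power claim, and SAP 3.1 plans no multiplicity adjustment. A reader might infer that the psychosocial comparisons are underpowered or biased, or that the baseline is ignored. The documents support none of these.

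**The size depends on undocumented inputs.** This also stands. A 0.5 SD shift is the standardised effect used for HbA1c, and nothing in the documents supports it for depression or distress. At 0.3 SD the caseness test has 42% power at most with either covariate, so the change would rarely alter a conclusion.

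**A binary covariate has merits.** This stands in part. It needs no linearity assumption on the logit scale, and its odds ratio reads directly as the effect given case status at entry. It also matches the PHQ-9 split used for subgroups in SAP 5.2.4. The odds ratio is non-collapsible, so changing the covariate changes the quantity reported. At ρ = 0.7, caseness 30% and shift 0.5 SD, the median log odds ratio was −1.14 with caseness and −1.28 with the score. With stand-in covariates the log odds ratio moved from −1.31 to −1.50 and the standard error rose from 0.59 to 0.65. The interval widens on the log scale, but the ratio still improves: 1.31/0.59 = 2.22 against 1.50/0.65 = 2.31. It would therefore be wrong to say that the binary covariate has no benefit or that the change has no downside.

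**The parallel with the HbA1c models is an inference.** Protocol 14.2.2 adjusts the HbA1c yes/no models for baseline HbA1c category, whereas the SAP specifies "adjustment for the baseline HbA1c and the other variables included in the minimisation allocation algorithm as covariates". A reader might conclude that the SAP has already moved from category to continuous baseline in its binary models. That is the natural reading, but the SAP does not say continuous, and the minimisation variable in SAP 2.2 is the category. The parallel is suggestive only.

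**Conclusion.** The point holds as a minor inefficiency. Under the assumptions stated, adjusting for baseline caseness instead of the baseline score costs about 1 to 7.5 points of power at a 0.5 SD shift and about 0.5 to 6 points at 0.3 SD. The loss is smallest at low correlation. The direction was the same in every setting with a non-zero effect, including a skewed score entered linearly. The exact size cannot be known from the documents, because it depends on the correlation, caseness rate and effect.

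The planned test is valid, and adjusting for baseline caseness is better than no baseline adjustment. The main analysis of both scales is unaffected.

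**What to change.** In the caseness paragraph of SAP 5.2.2, replace "adjusting for baseline caseness of the outcome" with *the baseline score of the outcome (PHQ-9 total score; T1-DDS mean-item score)*. State that the score enters linearly, with a transformation or spline if linearity on the logit scale is not tenable. Report the odds ratio as conditional on baseline score.

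Make the change before analysis. The two adjustments estimate different conditional odds ratios, and under SAP 2.6 the trial statistician is not blind to treatment group at the final analysis, so the choice should be on record beforehand.

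The cost is a few words and a SAP revision entry. No new data, visits or sample size are needed, and the protocol is not contradicted. What is given up is the direct reading of the odds ratio by case status at entry. A descriptive table of baseline by 24-week caseness in each arm would retain that information.

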#### **5.2.3 Sensitivity analyses**

Sensitivity analyses will examine robustness of the primary outcome results to assumptions regarding missing data by performing multiple imputation (see Section 5.3).

The primary outcome analysis will also be repeated having included additional covariates for the consideration of improved precision. These covariates will include age, sex, BMI duration of diabetes, deprivation index quintile.

Complier-Adjusted Causal Effect (CACE) will be used, implemented using an instrumental variables approach, to estimate the causal effect of the FSL device glucose monitoring relative to finger-stick glucose monitoring. Appropriate definitions of non-compliance (adherence) will be investigated within this sensitivity analysis, including the simple definition in the finger-stick monitoring arm of non-compliance equating to use of FSL device glucose monitoring for at least 10 days between the 3-month and 6-month outcome assessment.

Additional sensitivity analyses will be conducted to assess the impact of primary outcome data collected outside the visit window as specified in the protocol, that is:

- +/- 2 weeks of the planned visit date or
- +/- 4 weeks of the planned visit date.

Further sensitivity analyses will be performed to assess the potential impact of COVID-19 on the primary outcome. These will include the exclusion of participants whose treatment or outcome assessment was deemed severely impacted by COVID-19.

Finally, additional sensitivity analyses will be introduced to examine for the impact of protocol deviations or other unexpected events that may not have been captured in the protocol, including the impact on key secondary outcomes, where deemed necessary.

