7.3 Exclusion Criteria

1. Non-type 1 diabetes mellitus including those secondary to chronic disease
2. Any other physical disease or people with known severe mental illness (psychotic disorder, bipolar disorder, dementia, substance and alcohol dependence, learning disabilities, depression with active suicidal ideation) which are likely to interfere with the normal conduct of the study and interpretation of the study results as judged by the investigator
3. Current users of real-time glucose monitoring sensors or flash-glucose monitoring for more than 4 weeks within last 12 weeks
4. Initiation of medications/treatments known to interfere with glucose metabolism (e.g: metformin, SGLT2 inhibitors, GLP-1 agonists, Pramlintide) within the last 6 weeks or planning to start these medications within the next 6 months (patients on stable treatment is not an exclusion) or current or planned glucocorticoid use other than inhaled/ topical use.
5. Known or suspected allergy against insulin
6. Severe visual impairment
7. Complete loss of hypoglycaemia awareness
8. Patient receiving dialysis / pre-dialysis based on history
9. More than one episode of severe hypoglycaemia as defined by American Diabetes Association (30) in preceding 24 weeks as confirmed by clinical history or hospital notes; (severe hypoglycaemia is defined as an event requiring assistance of another person to actively administer carbohydrates, glucagon, or take other corrective actions including episodes of hypoglycaemia severe enough to cause unconsciousness, seizures or attendance

at hospital; children: severe hypoglycaemia is defined as an event associated with a seizure or loss of consciousness);

10. Total daily insulin dose ≥ 2 IU/kg/day
11. Pregnancy, planned pregnancy in the next 8 months, or breast feeding
12. Participant is using implanted internal pace-maker
13. Participants with medically documented allergy towards the adhesive (glue) of plasters or participant is unable to tolerate tape adhesive around sensor placement area
14. Serious skin diseases (e.g. psoriasis vulgaris, bacterial skin diseases) located at places of the body, which potentially are possible to be used for localisation of the glucose sensor)
15. Participant is currently abusing illicit drugs as judged by the investigator
16. Participant is currently abusing prescription drugs as judged by the investigator
17. Participant is currently abusing alcohol as judged by the investigator

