12.1 Procedures

12.1.1 Height and Weight

These will be recorded at the study initiation visit at screening, where possible..

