## 2.3 Sample size

Assuming a standard deviation of 0.8% and treatment difference of 0.4% - 128 participants (64 per each arm) with primary outcome will give 80% power to detect the difference between treatment groups at 2-sided type 1 error = 5%. Recruitment target is 180 participants (25 to 30 per centre) aiming for 150 to be randomised following the adherence run-in period, and allowing for 15% post-randomisation attrition.

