### 3 STATISTICAL PRINCIPLES

#### 3.1 Confidence intervals and P-values

All statistical tests will use a 2-sided significance level of 5% (unless otherwise specified). All confidence intervals presented will be 95% and two sided. No adjustment for multiplicity is planned.

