### 5.3 Missing data

Should we have more than 10% missing HbA1c at 24 weeks (or more than a 10% difference between missing data percentages in the two arms), multiple imputation will be used in order to implement a more complete ITT analysis of the substantive ANCOVA model. The imputation model will include baseline and 12-week HbA1c, all the baseline variables used in the outcome model and any other recorded variables found to be predictive of missing the 24-week outcome in exploratory analyses (via a logistic regression model, with terms included using a 10% significance level). A minimum of 50 imputations will be performed, although this will be increased if the percentage of missing data is greater than expected. We will perform multiple imputation by chained equations (MICE).

Complete cases analyses will be implemented for all secondary outcomes. Should we have up to 30% missing items for any subscale (or overall questionnaire if no subscales), the missing item will be imputed by the mean response of the rest items completed within participant for that particular subscale. If more than 30% missing items the response to this subscale will be set to missing, as will be the overall response of the questionnaire.

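### SAP 5.3 has no rule for a missing baseline covariate, so its complete-case rule drops randomised participants who have a follow-up outcome but no baseline value

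*SAP*

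**What the plan says.** **Missing data.** SAP 5.3 covers two situations: a missing 24-week HbA1c, and missing items within a questionnaire. For everything secondary it says: "Complete cases analyses will be implemented for all secondary outcomes". It gives no rule for a missing baseline covariate in a participant whose outcome is observed.

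**Models that need a baseline value.** SAP 5.2.2 adjusts the insulin-dose and psychosocial outcomes for their baseline level, and the PHQ-9 and T1-DDS caseness models for baseline caseness. SAP 5.4 does the same for finger-stick frequency, DTSQ and GMSS. SAP 3.3 says that all randomised participants are analysed in their allocated group.

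**The covariate-adjusted repeat.** SAP 5.2.3 says: "The primary outcome analysis will also be repeated having included additional covariates for the consideration of improved precision". The list is age, sex, BMI, duration of diabetes and deprivation quintile. The primary model in SAP 5.2.1 contains none of these.

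**Height and weight.** Protocol 12.1.1 says: "These will be recorded at the study initiation visit at screening, where possible". Protocol 9.2 lists both measurements and the BMI calculation at Visit 1 without that qualifier, while allowing the visit to be virtual. Exclusion 10 in protocol 7.3 ("Total daily insulin dose") is expressed per kilogram.

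**When the primary analysis is complete-case.** SAP 3.3 and 5.3 use complete cases unless more than 10% of 24-week HbA1c is missing, or the arms differ by more than 10%. Otherwise multiple imputation by chained equations (MICE) is used, with the baseline variables of the outcome model included.

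**The concern.** A regression on complete cases drops anyone with a gap in any covariate, not only those without an outcome. For the secondary models the SAP prescribes this outright. Participants who were randomised and supplied a follow-up value would leave the analysis because of something not recorded before allocation.

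Because baseline missingness comes before allocation, the arm comparison among those who remain is not biased by it. What is lost is information, and the analysed set is smaller than SAP 3.3 implies.

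The covariate-adjusted repeat exists to improve precision. If it lost participants through missing BMI, the loss could cancel the gain. Any difference from the primary result would also mix covariate adjustment with a change of participants.

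**Working it through.** **1. Design figures.** Inputs from SAP 2.3 and 3.1: "Assuming a standard deviation of 0.8% and treatment difference of 0.4" (percentage points of HbA1c), two-sided 5%, and "128 participants (64 per each arm) with primary outcome will give 80% power". The noncentral t gives power 0.801 at 64 per arm (the normal approximation asks for 63), so the plan's figure reproduces.

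**2. Which branch applies.** SAP 2.3 is "aiming for 150 to be randomised following the adherence run-in period, and allowing for 15% post-randomisation attrition". 128 of 150 observed means 22/150 = 14.7% missing, above the 10% trigger, so the planned attrition leads to multiple imputation for the primary analysis. The complete-case branch needs at least 150 × 0.90 = 135 observed. Secondary outcomes are complete-case in both branches.

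**3. Which secondary models are exposed.**
- Little exposure: HbA1c and sensor outcomes. Screening HbA1c is an eligibility criterion, protocol 9.4 requires run-in sensor data before randomisation, and the remaining adjusters are minimisation factors.
- Exposed: questionnaires, posted where necessary to remote participants (protocol 9.2.2), and insulin dose, whose diary covers Visits 4, 5 and 7 only (protocol 9.4.3), so its baseline rests on the Visit 1 record.
- The item rule can itself create gaps. GMSS Trust has three items (protocol Appendix 2). One skipped item is 1/3 = 33%, above the 30% limit, so Trust and the overall GMSS score are set to missing. At baseline, that removes the participant from both of those models.

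**4. Size for the secondary models.** Let m be the share of participants with a follow-up value but no baseline value, and ρ the baseline to follow-up correlation. Neither is given for these outcomes. I assume m of 5% to 20%, and borrow ρ of 0 to 0.7 from the HbA1c power table in protocol 14.1.
- Complete cases: variance ∝ (1 − ρ²)/(1 − m).
- Everyone kept, with mean plus missing indicator: variance ∝ (1 − m)(1 − ρ²) + m = 1 − (1 − m)ρ².
- SE ratio, complete-case to everyone kept = √{(1 − ρ²) / [(1 − m)(1 − (1 − m)ρ²)]}.

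| m | ρ = 0 | ρ = 0.5 | ρ = 0.7 |
|---|---|---|---|
| 5% | 1.026 | 1.018 | 1.002 |
| 10% | 1.054 | 1.037 | 1.007 |
| 20% | 1.118 | 1.083 | 1.024 |

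Example, m = 10%, ρ = 0.5: √[0.75/(0.90 × 0.775)] = 1.037. The ratio reaches 1 when ρ² = 1/(2 − m), that is ρ just above 0.7, so keeping everyone is at least as precise over the whole range considered.

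**5. Size for the BMI model, complete-case branch only.** SE ratio to the primary model = √[(1 − R²)/(1 − m)]. Here m is the share with HbA1c but no BMI, and R² is the partial R-squared of the added covariates. Both are assumptions.

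| m | R² = 0 | R² = 0.05 | R² = 0.10 |
|---|---|---|---|
| 5% | 1.026 | 1.000 | 0.973 |
| 10% | 1.054 | 1.027 | 1.000 |
| 20% | 1.118 | 1.090 | 1.061 |
| 30% | 1.195 | 1.165 | 1.134 |

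Break-even is m = R². A rough degrees-of-freedom allowance multiplies the variance by (N − 3)/(N − 3 − k), with k = 12 terms in the primary model (eight centres) and 20 in the extended one. At N = 135 and no missing BMI the SE ratio is √[(1 − R²) × 120/112]: 1.009 at R² = 0.05 and 0.982 at R² = 0.10. On that reckoning a weak covariate set gains nothing even with complete BMI.

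**The case against.** A reader might infer that the covariate-adjusted model is bound to be less precise than the primary one because it discards remote participants. The documents do not support that, for three reasons.

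- Precision falls only if the share lost exceeds what the added covariates explain (less once degrees of freedom are counted), and neither figure is given.
- At the planned attrition multiple imputation is triggered. A repeat done the same way, with the outcome model's baseline variables in the imputation, could impute BMI. The SAP does not say whether it would.
- Heavy BMI loss among remote participants is an inference. Protocol 9.2 lists the measurements for everyone, weight is sought again at Visit 3, and exclusion 10 needs a weight before randomisation. Nothing says that remote participants cannot report their own height and weight.

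Nor does exclusion 10 show a further defect: it points towards weight being available. It does not guarantee height, which BMI also needs.

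On the secondary outcomes, it can be said that questionnaires are scheduled at screening for all, that partial item loss is filled in, and that HbA1c and sensor models are barely exposed. That limits the size. It can also be said that the SAP lists DTSQ and GMSS under process evaluation rather than secondary outcomes. Protocol 10.2 does class them as secondary, and without a rule an ordinary regression would drop the same people. The complete-case instruction still stands as written and still removes participants with observed outcomes.

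**Conclusion.** The point holds for the secondary outcomes as a consequence of the SAP's own rule: a randomised participant with a follow-up value and no baseline value is dropped from the insulin-dose, psychosocial, DTSQ and GMSS models. The number affected is not documented. If 5% to 20% were affected and ρ lay between 0 and 0.7, standard errors would be 0.2% to 12% larger than with everyone kept. The departure from the set described in SAP 3.3 occurs whatever the size.

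For the BMI model the point is conditional. In the complete-case branch, participants with a measured HbA1c could be lost, which could offset the precision gain and would leave the two models fitted to different people. The direction depends on two undocumented quantities. It concerns one sensitivity analysis, and the primary estimate does not change.

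**What to change.** Add to SAP 5.3: where the outcome is observed, missing covariates recorded before randomisation, including the baseline value of the outcome, are handled identically in both arms. Continuous covariates take the overall mean plus a missing indicator. Categorical covariates, such as deprivation quintile and baseline caseness, take a separate missing category. Where multiple imputation is used, covariates in the model being fitted are imputed within MICE instead. N is reported for each model.

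This is sound because pre-randomisation values, and whether they are missing, cannot depend on allocation. It should therefore not be extended to values collected after randomisation.

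Separately, reconcile protocol 9.2 with 12.1.1 on how height and weight are obtained at a remote Visit 1.

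The cost is a short addition to the SAP and a few extra model terms. It needs no new data, so it can be adopted even if recruitment has finished.
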